Statistical power analysis: In doing the power calculation, we control for false discovery rate (FDR), a common method used in genome level analysis to control for multiple testing of a large number of genes. The statistical power is also a function of proportion of non-differentially expressed genes using the method developed by Liu and Hwang in 2007. Based on our feasibility study findings, we used 98% non-differentially genes and effect size of 1.5 for power calculation. With 50 chronic migraine (each serving as his/her own control), we will have 95% statistical power to detect effect size of 1.5, with stringent FDR of 0.001.

Figure 2. Power vs. Sample Size with $fdr=0.001$ and $\Delta/\sigma=1.5038$

Statistical analysis for main outcome measure: (A) Comparisons of targeted transcriptome from periosteal, muscles and fascia surrounding nerves will be performed between corresponding injected and not-injected tissues using Wilcoxon's Matched Pairs Tests.

Quality controls (QC), normalization and preprocessing analysis of genomics profiling data : Tissues genomics profiling data will be analyzed using the following major steps:

- (a) Quality control: We will first assign a quality measure for each sample based on nanostring standard QC criteria such as FOV counted, binding density, array mean signal, average background, and scaling factor using expert bioinformatician supervision. We will also check for reproducibility of the samples using correlation and signal-to-noise ratio (SNR) methods for replicate arrays. Low quality arrays will be excluded from further analysis.
- (b) Normalization: Normalization is the most critical step in the analysis, which is a transformation of signal values so that different chip results become comparable. The normalization will be performed in three steps: (i) Positive Spike in controls based normalization that will take care of signal variation due to different amounts of input RNA, (ii) Negative Spike in controls based background correction, (iii) Normalization based on signal values of house keeping genes from the experiments to bring all

the chips onto a similar expression level. The different normalizations and QC's will be performed using the Bioconductor R packages workflows.

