(c) Unsupervised analysis: To identify unbiased patterns of similarity, outlier arrays and batch effects, unsupervised learning technique will be performed on the normalized expression profiles of all genes. The unsupervised learning will be carried out using the Unweighted Pair Group Method with Arithmetic Mean (UPGMA), also referred to as hierarchical clustering. The assumption underlying these clustering techniques is that expression profiles that are proximate in Euclidean or correlation space are mechanistically related. Additionally attempt to identify outliers will be done using principal component analysis.

Identification of Botox signatures: In this analysis, we will consider the gene expression as the dependent variable and the indicator variable of group (e.g. Botox vs. No Botox) as the independent variable. The analysis will be performed using Linear Models for Microarray Data (LIMMA) as it employs an empirical Bayes approach for parameter estimation. To reduce the false positive, the significantly differentially expressed genes will be obtained using Benjamini and Hochberg multiple test corrected P value. The genes with P value < 0.01 and absolute fold change of at least 2 folds will be considered as differentially expressed. Due to differences in level of expression of gene in different tissues, we will perform separate normalization and signature identification for each tissue type.

Functional and Pathways analysis: The genes from different tissues will be further analyzed in the context of biological pathways, Gene Ontology (GO) and functional categories. The analysis will be performed using MATLAB, Bioconductor and commercial packages (e.g. Ingenuity pathways Analysis). Identifying significantly over-represented biological pathways is particularly valuable for understanding the underline mechanism of action of Botox.

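### The LIMMA model that calls genes names no patient term, although every patient supplies both an injected and an uninjected side

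*Combined protocol and SAP*

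**What the plan says.** The design is paired. Section 3.A describes removing equal amounts of corresponding tissue from both sides of the head, one side having been injected. The power statement in section 3.B rests on this: "With 50 chronic migraine (each serving as his/her own control". The main-outcome comparison, by Wilcoxon's matched-pairs test, "will be performed between corresponding injected and not-injected tissues".

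The signature step in the same section uses LIMMA, with gene expression as the dependent variable and "the indicator variable of group (e.g. Botox vs. No Botox) as the independent variable". It then gives the calling rule, with P values corrected by Benjamini-Hochberg (BH): "The genes with P value < 0.01 and absolute fold change of at least 2 folds will be considered as differentially expressed". Tissues are handled one at a time: "we will perform separate normalization and signature identification for each tissue type". The next step is stated as: "The genes from different tissues will be further analyzed in the context of biological pathways".

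Neither the protocol nor the appended IRB summary names a patient effect, a block or a within-patient correlation for this model.

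**The concern.** With the group indicator as the only regressor, LIMMA treats the two sides of one head as independent samples. Variation between patients, which cancels in a within-patient difference, then stays in the residual. If the two sides are positively correlated, which is plausible but not documented, the standard error of the Botox contrast is too large and the own-control advantage is lost at the step that calls genes.

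This matters because the P < 0.01 and 2-fold rule is the plan's only explicit definition of a differentially expressed gene. The paired Wilcoxon comparison has no significance level, FDR or fold-change cut attached, and the FDR of 0.001 belongs to the power calculation. The enrichment steps use hypergeometric tests, which need a list of called genes. A gene missed by LIMMA would therefore be expected to drop out of the mechanism-of-action analysis as well.

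**Working it through.** **Inputs from the documents.** 50 patients as own controls (power statement); up to 65 recruited (section 3.C); 98% null genes and effect size 1.5, given as 1.5038 in the power figure caption; calling rule BH P < 0.01 and |log2 fold change| >= 1.

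**Assumed, because the documents do not give them.** Within-patient correlation rho 0 to 0.7; equal per-side log2 SD; a true 2.5-fold change (log2 = 1.32); 1,000 genes.

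**1. The plan's own power figure.** The named FDR-based method solves pi0·a / (pi0·a + (1−pi0)·power) = 0.001 with pi0 = 0.98 and effect 1.5. For n = 50 it gives more than 99.9% in paired form and 99.8% (two-sided) in two-sample form with 50 per side. The stated 95% is not reproduced exactly, but it holds as a floor under either reading. At the planned effect, leaving out the patient term therefore costs almost nothing.

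**2. Standard errors.** With per-side SD s:
- group-only: s·sqrt(2/n)
- paired: s·sqrt(2(1−rho)/n)
- ratio: 1/sqrt(1−rho) = 1.20, 1.41, 1.83 at rho 0.3, 0.5, 0.7

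**3. Where the 2-fold cut decides anyway.** With 98% null genes and 95% power, BH at 0.01 corresponds to a per-gene alpha of 0.01 × 0.02 × 0.95 / (0.99 × 0.98) = 1.96e-4. The group-only critical t is 3.87 (98 df) at n = 50 and 3.84 (128 df) at n = 65. A gene observed at exactly 2-fold has t = 1/(s·sqrt(2/n)), so the P value starts to bind at s = 1/(t·sqrt(2/n)):
- n = 50: 1/(3.87 × 0.200) = 1.29
- n = 65: 1.49 (critical t unrounded)

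Below these SDs the 2-fold cut alone decides and the two models agree. Across 80 to 99% null genes and 20 to 95% power, the switch point runs from 1.1 to 1.8.

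**4. Simulated call rates.** Pairs of bivariate normal log2 values; 2% of 1,000 genes changed 2.5-fold; BH at 0.01, then the 2-fold cut; 300 data sets per cell (100 at SD 1.0). Ordinary t statistics were used, with n−1 df (paired) or 2n−2 df (group-only). Entries are the percentage of changed genes called, paired vs group-only.

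| n | SD | rho 0.3 | rho 0.5 | rho 0.7 |
|---|---|---|---|---|
| 50 | 1.0 | identical | identical | identical |
| 50 | 1.5 | 85 vs 69 | 93 vs 72 | 98 vs 77 |
| 50 | 2.0 | 38 vs 11 | 71 vs 9 | 92 vs 5 |
| 65 | 1.0 | identical | identical | identical |
| 65 | 1.5 | 93 vs 90 | 96 vs 94 | 99 vs 97 |
| 65 | 2.0 | 67 vs 36 | 88 vs 34 | 95 vs 27 |

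At rho 0.5 the SD of the within-pair difference equals the per-side SD. The 2.5-fold change is then 1.32/1.5 = 0.88 SD or 1.32/2.0 = 0.66 SD.

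**5. Planned effect under the full rule.** Taking 1.5038 as SDs of the difference or as per-side SDs, with SD 0.5 to 2.5, rho 0 to 0.7, both sample sizes and fixed alpha, the call rates differ by at most 0.1 point.

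**6. Panels with mixed SDs.** The SD 2.0 rows give every gene that SD, so few genes are rejected and BH tightens for all of them. At a fixed alpha of 1.96e-4 (SD 2.0, rho 0.5) the rates are 72 vs 23% at n = 50 and 88 vs 47% at n = 65. If only 10% of genes have SD 2.0 and the rest 0.8 (rho 0.5, 200 data sets), the SD 2.0 genes are called about 71 vs 22% at n = 50. Over all changed genes the capture is 97 vs 92% at n = 50 and 99 vs 94% at n = 65.

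**The case against.** The plan is silent rather than wrong. One sentence names the variables without a design formula and does not exclude blocking, and the same section twice describes the comparison as paired. The main-outcome test is already paired, the error is conservative, and nothing is lost at the planned effect. The losses need effects of roughly half that size, with correlations and SDs that nobody has documented. The most extreme contrasts come from giving every gene a high SD, and LIMMA's empirical Bayes shrinkage was not simulated. The plan also does not say outright that only called genes enter the pathway step.

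Most of this stands, and it limits the size of the point. The SD 2.0 rows are a worst case for a whole panel; in a mixed panel the overall loss is about 5 points, although the variable genes themselves still fall from about 71 to 22%. The effect of the shrinkage has not been bounded.

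The objection does not remove the point. The model's independent variable is named, and it is the group indicator alone. If blocking is intended, one phrase records it; if not, the pairing is discarded at the calling step. The doubt about downstream use is weak, because hypergeometric enrichment needs a gene list.

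**Conclusion.** The concern holds and should be fixed. As written, the gene-calling model ignores the pairing on which the design rests. With positive within-patient correlation it loses sensitivity for effects well below 1.5 SD in transcripts whose per-side log2 SD exceeds about 1.3 (n = 50) or 1.5 (n = 65). At SD 1.5 and rho 0.3 to 0.7 the loss is 16 to 21 points with 50 patients, but only 2 to 4 with 65. It is larger at SD 2.0 and absent at SD 1.0. False positives are not increased, and the paired main-outcome test is unaffected. The direction of the error follows from algebra once rho is positive. Its size depends on the assumed rho, SD, fold change and panel, and on ordinary rather than moderated t statistics.

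**What to change.** In the signature paragraph of section 3.B, state that LIMMA is fitted separately for each tissue with patient as a blocking factor plus treatment, and keep the BH P < 0.01 and 2-fold rule. Also state what happens when quality control leaves a patient with one usable side, since the plan says "Low quality arrays will be excluded from further analysis". There, treat patient as a random block through LIMMA's within-patient correlation, so that the remaining sample still contributes.

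The cost is one model term, with no new patients, samples or assays:
- **Degrees of freedom.** With a fixed block, residual df fall from 98 to 49 (n = 50) or from 128 to 64 (n = 65).
- **If rho is near 0.** The paired model does slightly worse. At SD 1.5 and a true 2.5-fold change, paired vs group-only call rates are 58 vs 65% (n = 50) and 83 vs 86% (n = 65).
- **Lost arrays.** A fixed block takes no treatment information from one-sided patients. If arrays are lost at random with probability q, 50 patients give 50(1−q)² complete pairs and 100q(1−q) one-sided patients. At q = 10% (assumed) that is about 40 and 9, and the fixed-block standard error is 2 to 4% larger than with a random block (rho 0.7 to 0.3). At q = 20% it is 32 and 16, and 4 to 8% larger.

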Identification of tissues and pathways that potentially drive Botox effects: The comprehensive network generated above will be further analyzed to pin-down the involved tissues and pathways. To reach this goal, an effort will be made to find a sub-network with highest number of alterations. Such subnetwork will be identified using HotNet package that considers gene as a unit heat source, and uses a diffusion process to derive "hot" subnetworks that contain more alterations than expected by random chance. *In principle, significant subnetworks are routinely determined by both the frequency of alteration of genes and the local topology of the subnetwork.* To identify a key pathway(s) in a top significant subnetwork, we will use the Biological pathway enrichment analysis. This analysis will be done using various modules of Bioconductor, which uses multiple corrected hypergeometric tests to determine significance of pathway or biological process affected.

C. Subject Selection

Patients diagnosed with chronic migraine (fulfill criteria for CM as defined in the ICHD-3 beta), especially those complaining about chronic muscle tenderness, are routinely considered good candidate to benefit from a surgery in which trapped nerves are decompressed. In routine clinical care, such patients are referred to [name] to determine whether or not they fit to undergo the nerve decompression procedure. Of great importance to the evaluation of the proposed study is the fact that the decision on whether or not to operate is unrelated to and independent of any academic study. Those deemed good candidate for the surgery would be presented with an option to hear about the study from [name], the plastic surgeon responsible for their well-being during the surgery and the one handling the discarded tissues. Those interested in hearing about the study will be presented with all the necessary details required by the Western IRB and then given the option to sign (or not to sign).

Accordingly, up to ~~50~~ 65 chronic migraine patients will be recruited to the study (if they are found fit to undergo the surgery) by [name], a certified plastic surgeon with enormous experience in performing these procedures.

Inclusion Criteria:

- Age 18-65 years
- Diagnosis of Chronic Migraine consistent with International Classification of Headache Disorders (ICHD-III) criteria, with a history of bilateral headache pain and chronic tenderness in neck muscles

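### Pathway p-values computed inside a HotNet-selected sub-network ignore that selection, and are too small wherever pathways follow the network

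*Combined protocol and SAP*

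**What the plan says.** The steps are in Section 3.B (Statistical Considerations) of the combined protocol and SAP.

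- *Identification of Botox signatures* defines an altered gene, separately by tissue, after Benjamini-Hochberg correction: "The genes with P value < 0.01 and absolute fold change of at least 2 folds will be considered as differentially expressed".
- *Functional and Pathways analysis* plans a pathway analysis that is not tied to any sub-network: "The genes from different tissues will be further analyzed in the context of biological pathways, Gene Ontology (GO) and functional categories".
- *Identification of tissues and pathways that potentially drive Botox effects* adds the network step. Its target is stated as "an effort will be made to find a sub-network with highest number of alterations". HotNet is described as deriving "subnetworks that contain more alterations than expected by random chance", and the plan adds that "significant subnetworks are routinely determined by both the frequency of alteration of genes and the local topology of the subnetwork".
- The same paragraph then places the pathway test inside the result: "To identify a key pathway(s) in a top significant subnetwork, we will use the Biological pathway enrichment analysis". The tool is one "which uses multiple corrected hypergeometric tests to determine significance of pathway or biological process affected".

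For these last two steps the plan gives no significance level, number of permutations or diffusion threshold. It does not say whether all sub-network genes or only the altered ones are tested, or against which reference set. It gives no null distribution that reflects the selection.

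**The concern.** A hypergeometric p-value is correct when the listed genes are, under the null, a random sample from the reference set. Genes in a HotNet sub-network are not: they are there because they are altered or lie close to altered genes in an interaction network. If curated pathways coincide with neighbourhoods of that network, a connected set shares pathways whatever Botox does. The test then partly measures the topology used to choose the genes. Multiplicity correction adjusts for the number of pathways tested, not for how the list was formed.

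At stake is the mechanistic conclusion. This step is meant to narrow the result to the pathways and tissues behind the Botox effect, and its p-values would overstate the evidence for whichever pathway is named.

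**Working it through.** **The plan's own figure.** None is given for this step. The 95% power in Section 3.B concerns the per-gene comparison and does not enter here.

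**Inputs.** From the plan: unit heat on each altered gene, diffusion, the sub-network with most alterations, then corrected hypergeometric tests. Assumed, because the documents are silent: 600 assayed genes; 30 pathways of 20 genes; a network with on average 3 links per gene inside its module and 2 outside; a diffusion threshold tuned to a sub-network of about 15 genes; Benjamini-Hochberg at 0.05. The number of altered genes is 12 or 30. The first matches the plan's 98% null genes: 600 × (1 − 0.98) = 12. Alignment is the share of genes whose pathway is kept equal to their network module; the remaining pathway labels are shuffled.

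**Why a few neighbours suffice.** Under random sampling the expected overlap of 15 genes with one pathway is 15 × 20/600 = 0.5. The hypergeometric tail for 4 or more shared genes is P(X ≥ 4) = 0.00097, below the strictest Benjamini-Hochberg step of 0.05/30 = 0.00167. Four of 15 genes in one pathway are therefore enough. At full alignment a network neighbour shares a gene's pathway with probability about 3/(3+2) = 60%, against 19/599 = 3.2% for a random draw.

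**Simulation with altered genes scattered at random.** There were 1,000 replicates per setting, and 999 permutations for the null distributions. Entries are the percentage of replicates with at least one significant pathway; each pair is 12 / 30 altered genes.

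| Procedure | Alignment 100% | 50% | 25% | 0% |
|---|---|---|---|---|
| A. All sub-network genes vs panel, no requirement on the sub-network | 91.7 / 94.8 | 43.0 / 46.2 | 11.3 / 9.3 | 2.1 / 1.8 |
| B. Only altered sub-network genes vs panel, no requirement | 26.3 / 34.2 | 7.8 / 8.9 | 2.9 / 2.5 | 1.9 / 0.9 |
| C. Full list of altered genes vs panel | 1.2 / 0.7 | 1.5 / 0.9 | 1.0 / 0.9 | 0.8 / 0.9 |
| D. As A, but sub-network must pass a 5% permutation test | 2.3 / 4.2 | 0.8 / 1.9 | 0.4 / 0.1 | 0 / 0 |
| E. Altered genes vs the sub-network as reference set | 0 / 0 | 0 / 0 | 0 / 0 | 0 / 0.1 |
| F. Selection and enrichment permuted as one pipeline, nominal 5% | 7.8 / 5.8 | 5.3 / 4.8 | 3.3 / 4.2 | 4.0 / 5.1 |

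Row A against row C isolates the selection step as the source. Row F averages (7.8+5.3+3.3+4.0+5.8+4.8+4.2+5.1)/8 = 5.0%.

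**What happens after the requirement in row D is passed.** At full alignment the sub-network passed by chance in 2.3% and 4.4% of replicates. A significant pathway followed in 2.3/2.3 = 100% and 4.2/4.4 = 95% of those; over all full-alignment settings run the range was 85-100%. At 50% alignment (pass rates 2.5% and 2.6%) the shares are 0.8/2.5 = 32% and 1.9/2.6 = 73%. At 25% (2.1% and 3.5%) they are 0.4/2.1 = 19% and 0.1/3.5 = 3%. These shares rest on few passing replicates.

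**Other settings.** A version with the same panel size and a sub-network of about 11 genes, without any requirement, gave false pathways in 94-100% (12 altered genes, within-pathway link probability 0.3), 80% (30 altered, 0.2) and 24% (30 altered, 0.1). It gave 0% when topology carried no pathway information, and 0-1% on the full altered list. A further simulation gave 66-100% without the requirement, about 2-8% with it at 5%, and 0-2% on the full list; 78-100% of sub-networks passing by chance returned a pathway. When one pathway was truly hit, a wrong pathway was also called in 12-73% of runs that passed, against 0-3% on the full list. Only ranges are given for that last simulation, so it is supporting evidence.

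**The case against.** The strongest reply is that the plan already guards against random scatter. Enrichment is run in a significant sub-network, defined as holding more alterations than chance would give. Row D shows that, enforced at 5%, this keeps the end-to-end false-pathway rate low. A reader might infer from row A that the plan would almost always report a pathway under random scatter; the documents do not support that, because row A leaves the requirement out. A reader might also infer that the sub-network is chosen by connectivity alone; the text says alteration frequency and topology together.

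This stands, but it does not settle the matter. No cut-off is stated, and the declared target, the sub-network with most alterations, exists in every data set. The requirement also answers a different question: whether altered genes cluster, not which pathway they represent. Where pathways follow the network, passing it leaves the pathway p-value with little power to discriminate.

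A second reply is that the inflation depends on choices left open. That is correct. Rows B and E, and the 0% column, show it shrinking or vanishing, and the plan's wording excludes neither B nor E. A third reply is that this is a late, tentatively worded step, with an ordinary pathway analysis planned before it. That also stands and limits the severity.

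**Conclusion.** The concern holds in a limited form. As written, the pathway p-values come from a test that ignores how the genes were selected, and they are anti-conservative to the extent that pathways follow the network. Under random scatter the false-pathway rate runs from near 0% to near 100% without an enforced requirement on the sub-network, and about 1-8% with one at 5% where pathways follow the network closely. Panel size, network, alignment, tested list and reference set are all assumed, so these figures show the possible size of the problem and do not predict this trial's error rate. There is no inflation if pathways do not follow the network or if the sub-network itself is the reference set.

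It would be wrong to infer that the study's main findings are compromised. The paired Wilcoxon comparison and the LIMMA signatures come before this step and do not use it. Severity is moderate.

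**What to change.** In *Identification of tissues and pathways that potentially drive Botox effects*, take pathway p-values from the full per-tissue list of differentially expressed genes, using the analysis already planned under *Functional and Pathways analysis* with the assayed genes as reference set. Label pathway results within the sub-network as descriptive.

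If sub-network pathway p-values are to be reported, calibrate them. Permute the gene alterations over the assayed panel, re-run HotNet selection and enrichment as one pipeline at least 1,000 times, and compare the observed minimum pathway p-value with that null distribution. State the cut-off for a significant sub-network, the tested gene list and the reference set in the same paragraph.

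The cost is SAP wording, computing time and fewer pathways called significant. No data collection changes. Permuting genes removes the selection problem only; like the full-list test, it does not allow for correlated expression between genes.
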